OAS-M: The OAS-M is a 25-item clinician-administered, semi-structured interview with nine subscales^{45, 47}. It was designed to evaluate various manifestations of aggressive behaviors in outpatients, including the severity, type, and frequency of aggressive behavior. The scale assesses three overall domains: Aggression (Verbal Aggression, Aggression Against Objects, Aggression Against Others, and Aggression Against Self), Irritability (Global Irritability and Subjective Irritability), and Suicidality (Suicidal Tendencies, Intent of Attempt, and Lethality of Attempt). Only the Aggression and Irritability subscales will be used in the current study. The two Irritability subscales are rated on Likert-type scales from 0 = none at all to 5 = extreme. The Aggression scale uses a different format in which each specific behavior is scored separately by frequency and then multiplied by assigned weights. For each Aggression subscale, seven specific behaviors are listed in order of severity and then weighted by their respective rank. The weighted frequencies are summed to form each subscale score. Subscale scores are then multiplied by their own assigned weight: Verbal Aggression by 1, Aggression Against Objects by 2, and Aggression Against Others and Self each by 3. Weighted subscales are added to obtain a final scale score for Aggression. Evidence for inter-rater and test-retest reliability has been documented for the OAS-M, with intraclass correlations (ICCs) of .91 and greater for inter-rater, and ICCs of .46 to .54 for test-retest reliability, and the OAS-M has demonstrated sensitivity to pharmacotherapy-induced changes in aggression^{47, 48}. The time frame of the OAS-M is restricted to the past week. The OAS-M will be administered by interviewers blinded to treatment condition.

Anger Consequences Scale (ACQ): The ACQ is a brief self-report measure developed to assess the frequency of negative anger-related behavioral consequences. Internal consistencies of .75 to .91 were reported on the original 42 item version; the revised version shortened the measure to 33 items based on factor analysis⁴⁹. This scale includes items not covered by the other anger measures, including for example, trouble with the law, driving recklessly, getting into an accident, damaging relationships, etc.

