Treatment Satisfaction: a brief 4 item measure adapted from the Treatment Satisfaction Form used in the NIMH Treatment of Depression Collaborative Research Program will be used to assess satisfaction with treatment.

Treatment Utilization: The Longitudinal Interval Follow-Up Assessment (LIFE) treatment section provides continuous recording of mental health and medical treatments⁵². For the latter, number of hospitalizations, days spent in hospital, and number of outpatient visits for non-mental health medical treatments are recorded for the time period covered. Types and amounts of all mental health contacts, including inpatient and outpatient treatment, are recorded on a monthly basis. All psychiatric medications, including dosages are recorded on a weekly basis (see Appendix 4 for list of medications). We will also assess all prescribed non-psychiatric medications, over the counter medications (including caffeine), and herbal and other supplements taken for any reason.

A baseline version (LIFE-Base) assesses mental health treatment received prior to entering the study. We will adapt the LIFE-Base to indicate whether prior treatment occurred before, during, or after deployment, and also to assess whether prior treatment focused specifically on anger or PTSD.

D. 7. Schedule of Assessments

The schedule of assessments is shown in Table 1. The CAPS and the SCID will be administered during the screening process prior to randomization to ensure that only eligible participants are entered into the study. Only eligible participants will complete the full CAPS and SCID and other pre-treatment measures. Assessments will be conducted at pre-treatment, during treatment (after sessions 4 and 8), end of treatment (week 12), and at three and six months following completion of treatment. We estimate that completion of the SCID and the CAPS will take 2 hours on average, and that the remaining pre-treatment measures will take about 2 ½ hours. The pre-treatment assessment will be conducted in 2 sessions. Mid-treatment assessments should take about 45 minutes. We estimate that post-treatment and follow-up assessments will take about 2 ½ hours on average.

We will aim to complete the post-treatment and follow-up assessments in a single

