All major variables will be screened for inconsistent or abnormal values, and continuous measures will be assessed for skewness and outliers. Transformations to improve normality may be applied to continuous variables. Missing data rates and patterns will be assessed; in particular, missing data rates by treatment group will be studied. Although randomization tends to produce well-balanced treatment samples⁵⁹ analyses will be carried out to determine any baseline differences between the treatment groups on demographic or other prognostic variables, using chi square analyses for discrete variables and ANOVA for continuous ones. If significant treatment group differences are found on potentially important baseline variables, these variables will be covaried in outcome analyses. Data from all randomized study participants will be used to compare the outcome of the two interventions on an intent-to-treat basis. Hypothesis tests will be two-tailed.

Participants will be counted in the intervention group to which they were randomized, regardless of the number of sessions they completed. We will make every attempt to complete a post-treatment and 3 and 6 month follow-up assessments on any participants who do not complete treatment. We will also conduct supplementary analyses including only those cases completing the full 12 sessions.

Aim 1: Investigate the effectiveness of CBI on primary measures of outcome

Hypothesis: Compared to SI, CBI will be associated with significantly larger reductions in anger and aggressive behaviors at post-treatment and at 3 and 6 month follow-ups.

Aim 2: Investigate the effectiveness of CBI on secondary measures of outcome

Hypothesis: Compared to SI, CBI will be associated with significantly more improvement in social functioning, occupational functioning, quality of life, and PTSD symptoms at post-treatment and at 3 and 6 month follow-ups.

For aims 1 and 2, we will use hierarchical linear modeling (HLM) for repeated measures to test for differences due to treatment condition, covarying for the baseline score of the dependent variable⁶⁵. The primary significance test will be the treatment group main

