Hypothesis: Change in arousal, cognitive, and behavioral domains of anger will mediate outcome for anger and functioning in the CBI condition.

In order to examine the mediating role of arousal, cognition, and behavior (NAS scales), we will use arousal, cognition, and behavior at post-treatment as mediators of the effect of treatment in predicting later anger and functioning at months 3 and 6. Therefore, these mediation tests will be fully prospective, as recommended by Kazdin & Nock⁶⁶, and as exemplified in prior mediational research done by [name]. These analyses will covary for the baseline scores of the mediators. Mediation of treatment effects through NAS scales will be tested using the Sobel test^{69, 70}. Simulation tests indicate that we will have more than 80% power to detect mediation when both paths have small to medium effect sizes⁷¹.

Aim 4: (Exploratory) Examine the effectiveness of CBI for those with and without PTSD. We will test for an interaction between CBI vs. SI and PTSD status by calculating simple slopes. Since we will not have 80% power to test this interaction, we will calculate treatment effect sizes separately for the PTSD and the no-PTSD cases.

G.3. Power Analysis

Power for our repeated-measures design was estimated using methods described by Faes et al.⁷¹. We obtained intervention effect sizes ranging from 0.78 to 1.12 in our pilot study, but given the small sample and the instability of effect sizes derived from pilot studies⁷² we have conservatively based our statistical power analysis for detection of medium effects.

We will use a two-sided alpha level of .025 in the primary and secondary outcome analyses to correct for the number of dependent variables; i.e., each DV will be tested individually with an alpha level of .025, keeping the study-wise alpha at .05. With this alpha level and an estimated 80% follow-up, a sample size of 120 will provide 90% power to detect a medium effect size of .60.

H. Time-Line

We anticipate the following time-line for the study:

Months	
0-6 Hiring, Training, IRB approvals	12-42 Follow-Up (6 month)
6-33 Recruitment	6-43 Data Entry and Management
6-36 Treatment	43-48 Final Data Analyses and Manuscript
9-39 Follow-Up (3 month)	Writing

I. Dissemination and Future Plans

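### The OAS-M Aggression model fixes only its own one-week baseline score as a covariate; naming one further baseline anger score already collected would be a nearly free gain in precision

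*Combined protocol and SAP*

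**What the plan says.** Section D.2 names two primary measures: the STAXI-2 Anger Expression Index and the OAS-M Aggression score. Blinded interviewers rate the latter. On its window, D.2 says: "The time frame of the OAS-M is restricted to the past week". On its stability, D.2 gives "ICCs of .46 to .54 for test-retest reliability". It does not say whether those figures belong to the Aggression score or to another OAS-M scale, or how far apart the two administrations were.

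For Aims 1 and 2, section G.2 specifies a hierarchical linear model "covarying for the baseline score of the dependent variable". The primary test is the treatment main effect over time. For the OAS-M it draws on five assessments: weeks 4 and 8, post-treatment, and months 3 and 6.

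Other covariates have four routes into the model:
- a significant baseline difference between arms (G.2);
- adjustment for imbalance (G.2);
- sex, if found necessary (section B, considerations on the criteria);
- comorbid disorders, if found necessary (section D.1).

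Table 1 also schedules the ACQ, the full STAXI-2 and the three NAS subscales at pre-treatment. D.2 describes the ACQ as "developed to assess the frequency of negative anger-related behavioral consequences", and STAXI-2 Trait Anger as a measure of how often angry feelings occur over time. Neither is described as limited to the past week, and neither is named as a covariate for the OAS-M model.

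**The concern.** A baseline covariate earns its place by predicting the outcome. If test-retest agreement of about one half applies to the Aggression score, a single past-week reading is a noisy marker of a person's usual level of aggression. A second baseline measure of anger over a longer window could then explain outcome variance that the first one misses.

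The plan holds such measures but admits them only through triggers. A trigger based on chance imbalance brings in variables because the arms happen to differ, not because the variables are prognostic. It therefore does not secure the gain, and it makes the content of the primary model depend on the data. At stake is the width of the interval on the one primary outcome rated by blinded interviewers.

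**Working it through.** **1. The plan's own power figure.** Section G.3 states: "We will use a two-sided alpha level of .025 in the primary and secondary outcome analyses". Assuming that four in five participants are followed up, it claims that "a sample size of 120 will provide 90% power to detect a medium effect size of .60". Eighty per cent of 120 is 96, or 48 per arm if allocation is 1:1 (assumed; no ratio is stated). The power of a plain two-sample comparison is Φ(d/√(2/n) − z), with z = 2.241 for two-sided .025.
- 0.60/√(2/48) = 0.60/0.2041 = 2.939, and 2.939 − 2.241 = 0.698. Power is 75.7%.
- G.3 used a repeated-measures method but states no within-person correlation, number of visits or covariate R². Supplying such values can reach about 90%. For example, the mean of three visits with correlation .54 and no baseline covariate gives 90.1%.
- So 90% is attainable but cannot be verified, and it is not shown to be wrong.

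**2. What the planned adjustment already does (model assumed).** Let one OAS-M score have variance 1, made of a stable part with variance ICC plus weekly noise. Let s be the correlation between a person's stable level at baseline and later.
- Variance of the five-visit mean: ICC + (1 − ICC)/5. At ICC .50 this is .60.
- Removed by baseline OAS-M: (s × ICC)². At s = 1 this is .25.
- Residual: .60 − .25 = .35, a 42% reduction (.25/.60).

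**3. Adding one more baseline score.** Let it correlate r with the stable level (assumed; the documents give no figure), and write c² = r² × ICC. The further variance removed is s² × c² × (1 − ICC)² / (1 − c²). At ICC .50, r = .5 and s = 1, c² = .125. The gain is .125 × .25/.875 = .0357, and .0357/.35 = 10.2%.

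Reduction in residual variance at ICC .50:

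| r with stable level | s = 1.0 (residual .35) | s = .8 (residual .44) | s = .6 (residual .51) |
|---|---|---|---|
| .3 | 3.4% | 1.7% | 0.8% |
| .5 | 10.2% | 5.2% | 2.5% |
| .7 | 23.2% | 11.8% | 5.7% |

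At ICC .46, r = .7 and s = 1 the figure is 23.8%. The range is therefore about 1% to about 24%. The interval narrows by 1 − √(1 − .01) = 0.5% to 1 − √(1 − .24) = 13%.

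**4. A second parameterisation.** Let the added score correlate .2 to .6 with every single OAS-M score, and let OAS-M scores correlate .46 to .54 with each other. The reduction is 1.2% to 20.8% for a single visit and 2.6% to 46.0% for the five-visit mean. The 46.0% needs a correlation of .6/√.46 = .88 with the stable level, which is too optimistic to rely on. The direction is the same throughout; the size follows the assumption.

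**5. Why no power gain is quoted.** Put the stated inputs (48 per arm, d = .60 in single-score SD units, two-sided .025) into the model of step 2 at ICC .50, with no added covariate:
- s = 1: 2.939/√.35 − 2.241 = 2.727, or 99.7%
- s = .8: 2.939/√.44 − 2.241 = 2.190, or 98.6%
- s = .6: 2.939/√.51 − 2.241 = 1.875, or 97.0%

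A single visit with baseline adjustment gives 2.939/√.75 − 2.241 = 1.153, or 87.5%. The starting power thus depends on choices that G.3 does not state.

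**The case against.** The strongest reply is that the plan already adjusts for the most natural covariate, and that this adjustment does real work. At ICC .50 it removes half of the stable variance (.25 of .50). Under the same model, power for the five-visit effect is already 97% or more, and adding a covariate with r of .5 to .7 raises it by less than one point. This stands. A reader might infer that baseline OAS-M removes little, or that the trial gains several points of power over 90%. The documents support neither: the first conflicts with the arithmetic, and the second attaches an assumed model to a 90% whose inputs are unstated.

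The size of the gain is also assumed. The ICC is not tied to the Aggression score or to an interval, so reading half of the score as weekly noise is an assumption. The ACQ is self-reported, measures consequences, and covers items that the other anger measures do not. Its link with an interview-based weighted count of acts may be weak. This stands too, and it is why the range starts near 1% and no one scale is insisted on.

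It would be too strong to say that the model can adjust for nothing else, since four conditional routes exist. But all four are conditional, and none fixes a covariate for its prognostic value.

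A reader might also infer that a second pre-treatment OAS-M interview is needed, since "The pre-treatment assessment will be conducted in 2 sessions". The documents do not support this. They give no spacing between those sessions, and it would add an interview to a baseline of about 4½ hours (2 hours for the SCID and CAPS plus about 2½ for the rest).

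The objection does not remove the central point: a named covariate secures whatever gain exists at almost no cost, and a chance-imbalance trigger does not.

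**Conclusion.** The point holds as a minor missed efficiency. No covariate beyond baseline OAS-M Aggression is fixed in advance for its prognostic value, although suitable scores are collected on the same schedule. Residual variance would fall by about 1% to about 24%. That range assumes an ICC of .46 to .54 for the Aggression score, a correlation of .3 to .7 between the added score and the stable level, and baseline-to-later stability of .6 to 1. Values outside those ranges would give other results, and the documents cannot settle which apply.

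A reader might infer that the treatment estimate is biased or that the stated power is wrong. Neither follows. In a randomised comparison, omitting a prognostic covariate from this linear model costs precision, not validity, and the 90% is unverifiable rather than refuted.

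**What to change.** In G.2, under Aim 1, state that the OAS-M Aggression model will include baseline OAS-M Aggression and one further named baseline anger score, entered whether or not the arms differ on it. ACQ total and a STAXI-2 score are both candidates, and the documents do not show that either predicts better. The pilot recorded both the STAXI-2 and the OAS-M, so it could inform the choice, with caution given its small sample.

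The choice must be fixed before arm-level outcomes are seen. The protocol version is dated 11/28/18, after the stated study end of 07/31/2018, so the sponsor should confirm that this condition can still be met. If it cannot, the adjusted model should be reported as a labelled sensitivity analysis.

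The cost is SAP wording and one degree of freedom, with no new data, visits or participant burden.

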- Arousal reduction, including diaphragmatic breathing, and guided imagery training
- Cognitive restructuring of anger schemas (identification and modification of beliefs and interpretations)
- Behavioral coping strategies (training in communication, assertiveness, and strategic withdrawal)
- Inoculation training (practicing the cognitive, arousal regulatory, and behavioral coping skills while visualizing progressively more intense anger-arousing scenes from personal hierarchies).

E.3. Supportive Intervention Control

The Supportive Intervention adapted for the pilot study included the same “Battlemind” psychoeducation as the CBI condition. Following the psychoeducation component, the rest of the intervention focuses on providing support and using problem solving strategies to help in managing behavior and feelings in current day-to-day life. Cognitive behavioral interventions are excluded. In addition to the exclusion of cognitive or behavioral strategies, SI is less structured; the patient has more input into the agenda of the sessions.

E.4. Therapist Selection, Training and Supervision

Therapists will be Ph.D. level psychologists or masters level clinical social workers with prior experience in cognitive behavioral therapy and prior experience treating PTSD patients. Therapists will receive training in both interventions. There are advantages and disadvantages to using the same or different therapists for study conditions. The primary concern with using the same therapists is the possible effect of a different level of enthusiasm and investment in the active treatment condition, which can bias results. However, bias can just as easily occur when therapists are assigned to deliver different treatment conditions. Our experience in the pilot study was that therapists appeared to be equally comfortable with both conditions, and ratings indicated adherence to the manual. Retention was slightly higher in the SI condition. An advantage of using the same therapist for both conditions is reduction of between treatment variance associated with therapist effects. Another advantage is the increased flexibility of assigning study participants to therapists to facilitate accommodation of study participants’ availability for appointments.

Initial training will be didactic, involving two days of instruction for CBI, and one for SI. Drs. [name] and [name] will conduct the didactic training for both conditions. Training will include disguised case examples derived from the pilot study sessions and role plays of interventions. Following the didactic training, each therapist will have one CBI training case, with weekly supervision based on review of audio recorded sessions. The training case must complete a minimum of 8 sessions to count. If the therapist is judged to be sufficiently competent, he or she will be approved to see study participants. This judgment will be based on mutual agreement by Drs. [name] and [name] who will supervise therapists, and on consistent ratings of adherence (75% of strategies

implemented across sessions rated). All therapy sessions for study participants in both conditions will be recorded. For the first two study cases for each therapist, every session will be reviewed and feedback will be provided weekly. Supervision will become less frequent with subsequent cases, although a minimum of three sessions will be reviewed for each case and feedback provided as needed.

E.5. Adherence Monitoring

Current standards in psychosocial treatment research require monitoring of therapist behavior and interventions to ensure treatment fidelity (i.e., that therapists are delivering the interventions specified in the manual and not using interventions that are not part of the treatment). In the proposed study, the first objective is particularly important for the Cognitive Behavioral Intervention, and the second is particularly important for the Supportive Intervention. We have developed adherence scales for both conditions, and findings from our pilot work showed good adherence in both conditions. Adherence ratings for both conditions will be completed by research study staff, and will include three sessions (early, middle, and late session) for each study participant. Ten early sessions will also be rated by [name] to establish reliability with research study staff.

F. Design Considerations

F.1. Treatment Format

The treatment we are studying is delivered in an individual format. An alternative choice would be to test the efficacy of a group format, which could be more cost-effective. We decided to use an individual format for several reasons. First, many patients with anger problems are unwilling to participate in group treatment. Second, the logistics of group interventions can be challenging, given the need to find a time that all potential group members can make. This may be particularly for OEF/OIF/OND veterans who often have time restrictions due to work and family. Further, in practice since groups are typically 10 to 12 weeks long, new veterans often have to wait until another group is available. Third, the intervention in the proposed study includes an imaginal exposure component, which would be difficult to implement in a group format. Finally, it is possible that individual delivery of anger treatment may be more effective than group delivery given the greater amount of time and more intensive focus that is possible in individual treatment. If CBI is found to be effective compared to SI, the next step would be to compare individual and group delivery of CBI.

F.2. Control Condition

Selection of control groups for psychosocial treatments is complex. Unlike medication trials, it is not possible to derive true “placebo” conditions that control for all aspects of the treatment delivery except the active ingredient (drug). A variety of control conditions have been used in behavioral treatment research, but there is no consensus regarding an optimal or standard control condition. There is increasing recognition that the design and selection of an optimal control condition depends upon the particular intervention being studied and the research question being addressed. One important consideration is how

much is known about the treatment being studied. Rounsaville and Onken⁶² outline a three stage framework including an initial stage (feasibility, pilot studies), RCTs / efficacy trials, and effectiveness studies. The proposed study would be considered a stage 2 efficacy trial according to this model; for such trials non-specific comparison designs have been recommended⁶³. In addition to controlling for passage of time, testing, statistical regression towards the mean (all of which may be controlled for by a wait-list control), a non-specific comparison condition controls for the aspects of therapy that characterize most forms of therapy and are distinct from the hypothesized active mechanisms of the treatment being studied. This type of control allows for inferences about the benefits of the specific treatment interventions, beyond the benefits of for example, meeting with a therapist, receiving attention and support, and expectations of improvement. The control condition proposed for the current study, which was adapted from the control condition used in the CSP clinical trial testing the efficacy of prolonged exposure⁵⁸, was designed to achieve this goal.

A treatment as usual control condition in some settings might serve the same purpose, if the “usual treatment” is clearly defined and consistently used, and does not include the hypothesized active mechanisms of the treatment being studied. In the setting for the proposed study, however, treatment as usual is not uniform, includes a range of providers, and could include a range of interventions, including medication only, group therapy, and/or individual therapy possibly including some aspects of cognitive or behavioral interventions. Because treatment as usual may vary in different settings, the findings could have limited generalizability. Even with careful assessment of type and dose of any additional treatment received in both conditions, we are concerned that the heterogeneity of treatment and the potential overlap of some cognitive behavioral interventions would make it more difficult to achieve the goal of allowing inferences about the efficacy of the specific cognitive behavioral interventions included in CBI.

G. Data Management and Analysis

G.1. Data Management

Research study staff will oversee data management procedures. Study data will be collected and managed using REDCap electronic data capture tools hosted at the Department of Veterans Affairs. REDCap (Research Electronic Data Capture) is a secure, web-based application designed to support data capture for research studies. Through REDCap, participants are able to respond to survey items electronically and additionally research study staff can manually enter responses. All study software and licensing, such as SPSS IBM (which will be used for data analyses) will be managed by PVAMC IT and IRM. For data that is entered manually, the project coordinator will be responsible for initial editing and correction of forms before they are data entered by the research assistant. As forms are entered into the master database, they will be checked against the participant tracking file to assure that all data that are gathered have been data entered. The data will be verified after entry and verification status will be tracked by the software. Validity checks will also be done as the data are entered, and questions or problems will be resolved by discussion between research study staff and the Interviewer. All data will be received stripped of personal identifiers. Because of the sensitive nature

of some of the data gathered, a number of precautions will be taken to prevent disclosure of information to unauthorized parties: (1) data sheets will be stored in locked offices of [name] (PI), building 32 of the PVAMC) (2) data will be entered in coded form, (3) data will be stored on a secure server behind the VA firewall (\vhaproapp12\Research_Protocols\[name]\Anger-R), (4) data will be protected from unauthorized access by passwords, (5) information that might potentially allow an individual participant to be identified will not be allowed in any publications or reports sent to individuals outside the study, (6) all employees who are to handle data will be trained in confidentiality policies and procedures, and (7) all data-related incidents will be reported to the local ISO and PO per VA policy. Study files will be maintained in accordance with the Department of Veterans Affairs Record Control Schedule 10-1. Data protection and precaution measures are further detailed in the Protocol Appendix – ISO (see page 31).

G.2. Data Analysis

All major variables will be screened for inconsistent or abnormal values, and continuous measures will be assessed for skewness and outliers. Transformations to improve normality may be applied to continuous variables. Missing data rates and patterns will be assessed; in particular, missing data rates by treatment group will be studied. Although randomization tends to produce well-balanced treatment samples⁵⁹ analyses will be carried out to determine any baseline differences between the treatment groups on demographic or other prognostic variables, using chi square analyses for discrete variables and ANOVA for continuous ones. If significant treatment group differences are found on potentially important baseline variables, these variables will be covaried in outcome analyses. Data from all randomized study participants will be used to compare the outcome of the two interventions on an intent-to-treat basis. Hypothesis tests will be two-tailed.

Participants will be counted in the intervention group to which they were randomized, regardless of the number of sessions they completed. We will make every attempt to complete a post-treatment and 3 and 6 month follow-up assessments on any participants who do not complete treatment. We will also conduct supplementary analyses including only those cases completing the full 12 sessions.

Aim 1: Investigate the effectiveness of CBI on primary measures of outcome

Hypothesis: Compared to SI, CBI will be associated with significantly larger reductions in anger and aggressive behaviors at post-treatment and at 3 and 6 month follow-ups.

Aim 2: Investigate the effectiveness of CBI on secondary measures of outcome

Hypothesis: Compared to SI, CBI will be associated with significantly more improvement in social functioning, occupational functioning, quality of life, and PTSD symptoms at post-treatment and at 3 and 6 month follow-ups.

For aims 1 and 2, we will use hierarchical linear modeling (HLM) for repeated measures to test for differences due to treatment condition, covarying for the baseline score of the dependent variable⁶⁵. The primary significance test will be the treatment group main

effect over time, though there will also be a test for the time by treatment interaction. Significant time by treatment interactions will be followed up by post hoc tests at specific assessment points by calculating simple intercepts, simple slopes, and regions of significance. Relevant covariates will be included to adjust for any imbalances across treatment conditions.

Missing data will be dealt with as follows. HLM analyses can include cases with some time points missing. In the primary analysis, we will include all cases with at least 3 of the 5 outcome time points (4 & 8 weeks, posttreatment, and 3 & 6 months) non-missing. Then, we will conduct a sensitivity analysis including all randomized participants, in which any missing outcome values will be filled in with baseline scores, which is an extreme assumption. Consistency of results from the two approaches will bolster the credibility of the primary analysis.

The primary dependent variables for aim 1 are the STAXI-2 Anger Expression Index, and the OAS-M Aggression Scale score. Outcome on these measures is assessed at 4 and 8-week points during treatment, at post-treatment, and at 3 and 6 months follow-up assessments. DVs for aim 2 include two LIFE scales (global social and work functioning), the Outcomes Questionnaire total score, the WHOQOL-BREF total score, and the CAPS total score. Outcome on these measures is assessed at post-treatment and 3 and 6-month follow-up assessments.

For aims 1 and 2 the alpha will be set at .025 to account for multiple dependent variables.

Supplementary post-treatment outcome analyses will be conducted using collateral measures (including the STAXI-II, Anger Control Scale and Modified Overt Aggression Interview). We will calculate Pearson correlations of participant and collateral scales as an indication of agreement. If outcome analyses based on collateral measures are consistent with analyses of participant measures, this would bolster the validity of the participant outcome findings. Divergent findings could be due to multiple factors that could influence the validity of the participant and the collateral reports. In this case we will conduct analyses using integrated collateral and participant scores, calculated by averaging the participant and collateral responses to each item.

Aim 3: (Exploratory) Examine hypothesized mechanisms of action of CBI

Hypothesis: Change in arousal, cognitive, and behavioral domains of anger will mediate outcome for anger and functioning in the CBI condition.

In order to examine the mediating role of arousal, cognition, and behavior (NAS scales), we will use arousal, cognition, and behavior at post-treatment as mediators of the effect of treatment in predicting later anger and functioning at months 3 and 6. Therefore, these mediation tests will be fully prospective, as recommended by Kazdin & Nock⁶⁶, and as exemplified in prior mediational research done by [name]. These analyses will covary for the baseline scores of the mediators. Mediation of treatment effects through NAS scales will be tested using the Sobel test^{69, 70}. Simulation tests indicate that we will have more than 80% power to detect mediation when both paths have small to medium effect sizes⁷¹.

Aim 4: (Exploratory) Examine the effectiveness of CBI for those with and without PTSD. We will test for an interaction between CBI vs. SI and PTSD status by calculating simple slopes. Since we will not have 80% power to test this interaction, we will calculate treatment effect sizes separately for the PTSD and the no-PTSD cases.

G.3. Power Analysis

Power for our repeated-measures design was estimated using methods described by Faes et al.⁷¹. We obtained intervention effect sizes ranging from 0.78 to 1.12 in our pilot study, but given the small sample and the instability of effect sizes derived from pilot studies⁷² we have conservatively based our statistical power analysis for detection of medium effects.

We will use a two-sided alpha level of .025 in the primary and secondary outcome analyses to correct for the number of dependent variables; i.e., each DV will be tested individually with an alpha level of .025, keeping the study-wise alpha at .05. With this alpha level and an estimated 80% follow-up, a sample size of 120 will provide 90% power to detect a medium effect size of .60.

H. Time-Line

We anticipate the following time-line for the study:

Months	
0-6 Hiring, Training, IRB approvals	12-42 Follow-Up (6 month)
6-33 Recruitment	6-43 Data Entry and Management
6-36 Treatment	43-48 Final Data Analyses and Manuscript
9-39 Follow-Up (3 month)	Writing

I. Dissemination and Future Plans

The proposed study is a randomized clinical trial of the efficacy of a cognitive behavioral intervention (CBI) for the treatment of trauma related anger in OEF/OIF veterans. Prior to the start of the study, we will register with ClinicalTrials.gov. This website contains over 100,000 trials sponsored by a variety of federal and private industry sources, and receives over 50 million page views per month and over 65,000 visitors daily.

Dissemination will include submission of the study findings to a peer-reviewed journal. The findings will also be presented at professional conferences, such as the International Society for the Study of Traumatic Stress, and appropriate VA and Department of Defense conferences. If CBI is found to be significantly superior to the supportive therapy control (SI), we will consider multiple methods for further dissemination. We will create a fact sheet describing the intervention and findings and circulate to VA, National Guard and other military officials, and relevant DOD programs such as the Defense Centers of Excellence. The manual will be made available free of charge. We could begin dissemination efforts by implementing the treatment at the Providence VAMC. We would

provide the manual and training to the mental health clinicians in the PTSD and Returning Veterans clinics, and encourage the use of relevant self-report outcome measures to provide an index of effectiveness in a naturalistic setting. A proposal of a multi-site study through the Cooperative Studies Program would be considered, to more formally test the effectiveness of the intervention across multiple VA settings.

5. Privacy and Confidentiality

Every effort will be taken to protect the confidentiality of the participants in this study. All information about the veteran that is gathered during the research (including recordings) will be kept strictly confidential. However, veterans will be informed that there is no guarantee that the information gathered during the research cannot be obtained by legal process or court order. Furthermore, veterans will be informed that complete confidentiality cannot be promised to subjects, particularly to subjects who are military personnel, because information bearing on their health may be required to be reported to appropriate medical or command authorities. Additionally, federal and non-federal monitoring agencies such as the Department of Veterans Affairs may also access the veteran's research records related to this study to monitor the security of the trial. All data will be received stripped of personal identifiers. Measures will be identified with a study ID number not based on a personal identifier. A cross-index of names and ID numbers will be stored in a separate locked location from all data. Data entry and management will take place in VA offices in Bldg. 32. Additional precautions include: (1) Data sheets will be stored in locked offices, (2) data will be entered in coded form, (3) data will be stored in computer files on the secure Research Server in Bldg 32 and protected from unauthorized access by passwords, (4) information that might potentially allow an individual participant to be identified will not be allowed in any publications or reports sent to individuals outside the study, and (5) all employees who are to handle data will be trained in confidentiality policies and procedures. Records will be maintained per Veterans Affairs Record Control Schedule 10-1.

